The purpose of this study is to further investigate the role of CRT in the treatment of adolescent AN. The goal of this study is to determine whether or CRT increases flexibility in adolescents or parents, if this increase is more than what is observed in FBT alone, and what the dose of CRT is needed to increase flexibility.

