2.1 Primary Objective (or Aim)

Aim 1: To identify whether or not it more impactful to add a parent or adolescent component of CRT to standard FBT. We hypothesize that both adolescents and parents who receive CRT will have greater increases in cognitive flexibility than those who receive FBT alone. We will examine magnitude of change in cognitive flexibility across groups.

Aim 2: To determine the dose of CRT needed to lead to a medium effect size (increase in cognitive flexibility). We will examine the dose of CRT needed to obtain an increase in cognitive flexibility equal to a medium effect.

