6 STATISTICAL CONSIDERATIONS

6.1 Primary Endpoint

Aim 1: To identify whether or not it more impactful to add a parent or adolescent component of CRT to standard FBT. To assess if CRT engages the target, we will use mixed 3 (treatment) x 2 (time) Multivariate Analysis of Covariance (MANCOVA): one for adolescents, one for mothers, and one for fathers. The covariate for all analyses is total IQ on the WASI. Dependent variables are as follows: Trails Number-Letter Sequencing, Inhibition, Inhibition/Switching, Correct Response Shifting, Category Switching, or Description 1 or 2 and Shift on the BRIEF-2. We will follow these steps:

1. Conduct omnibus MANCOVA and evaluate significance. If not significant, stop and move to next analysis.
2. If the omnibus test is significant, we will conduct individual 2 (treatment) X 2 (time) Analysis of Covariance (ANCOVA) to determine which dependent variable had significant change, with IQ again as the covariate.
3. Each assessment of the target (DV) will be examined. Results will inform the Go/No-Go Decision as described in Table 6.

These three steps will be repeated for adolescents, mothers, and fathers. We will include all three groups in the initial MANCOVA and follow-up with planned comparisons (ANCOVA) of FBT vs the appropriate CRT condition. In all analyses, we will focus on the within and between-group effects, examining interaction effects are not necessary to evaluate the target. As we have chosen measures demonstrated to change with CRT,^{40,87-90} we will maintain $\alpha=0.15$ for each analysis.⁹¹ We do not expect adolescents whose parents receive CRT or parents whose adolescents receive CRT to demonstrate increases in flexibility. However, should the planned ANCOVAs not be significant, we will be able to explore other possible group differences. Additionally, we will explore the relationship between dependent variables via discriminant analysis. These additional methods to examine the data will not factor into the Go/No-Go decision, but will enhance the depth of our understanding of the data and contribute to our understanding of neurocognition in AN.

Aim 2: To determine the dose of CRT needed to lead to a medium effect size. Some research indicates that ≥ 8 sessions of CRT are necessary for improvement in cognitive flexibility with AN.⁹² It is unknown how many sessions will be needed for significant change in parents of

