6.4 Sample Size and Power

Power analysis Aim 1. In the initial phase of the proposed project (R61), our sample size estimation is based on a mixed MANCOVA design with two repeated measures from baseline to end-of-treatment (EOT; within subjects component) and three groups (CRT_P, CRT_A, and FBT; between subjects component). Based on a review of the literature, we are powering for a medium effect size. Our effect size estimate is Cohen's f statistic.⁹⁸ This effect size estimate is a ratio of variation explained to that unexplained by the model (treatment groups), and is expressed as

follows: $f = \sqrt{\frac{\eta^2}{(1-\eta^2)}}$, where $\eta^2 = \frac{\sigma_{model}^2}{\sigma_{Total}^2}$; proportion of variability due to the model.^{99,100}

Heuristics for small, medium, and large effect sizes are .1, .25, and .4, respectively. We selected an alpha of 0.15, given the nature of the study and the difficulty in recruiting participants from a low prevalence condition. Alpha of 0.15 is essential to provide adequate power for this study.⁹¹ As any analysis powered for a medium effect will also be powered for a large effect, we only highlight the expected medium effect. For all analyses, we specified an $\alpha=0.15$, two time points, and a correlation between measures of .3 (based on unpublished data). The anticipated N accounts for dropouts (i.e., number enrolled will be higher).

Power analysis Aim 2. Using Mplus 7.2,⁹⁴ we conducted a LGCM Monte Carlo simulation with 1000 replications^{94,101-103} to determine power to identify CRT_{P/A} dosage based on a half standard

deviation increase (rate of change; slope) from baseline (effect size) above FBT. With 15 participants in 3 groups across 5 time points, parameter and standard error bias were $\leq 5\%$, confidence interval coverage $\geq 90\%$, and power = 0.59.

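### Aim 1 sets aside the treatment-by-time term, although that term is its stated hypothesis: a greater increase with CRT than with FBT alone

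*Combined protocol and SAP*

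**What the plan says.** Section 2.1 hypothesises that "both adolescents and parents who receive CRT will have greater increases in cognitive flexibility than those who receive FBT alone" and adds: "We will examine magnitude of change in cognitive flexibility across groups". Section 1.3 frames the same question: whether CRT raises flexibility, and "if this increase is more than what is observed in FBT alone".

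Section 6.1 gives the analysis. A 3 (treatment) by 2 (time) MANCOVA is run separately for adolescents, mothers and fathers. If it is significant, 2 by 2 ANCOVAs of FBT against the relevant CRT arm follow, "to determine which dependent variable had significant change, with IQ again as the covariate". The only covariate is WASI IQ, and alpha is 0.15 per analysis. The section then says: "In all analyses, we will focus on the within and between-group effects, examining interaction effects are not necessary to evaluate the target". On the use of the findings it says: "Results will inform the Go/No-Go Decision as described in Table 6".

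Section 6.4 describes the design as "two repeated measures from baseline to end-of-treatment" in three groups, and assumes "two time points, and a correlation between measures of .3 (based on unpublished data").

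**The concern.** A greater increase than under FBT is a difference between arms in change over time. In a two-time-point mixed model that is the treatment-by-time term, which Section 6.1 declares unnecessary. Two effects remain.

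- **Within (time) effect.** This averages change over all arms, FBT alone included. A gain shared by every arm makes it significant without any contribution from CRT. Such a gain is plausible: Section 3.3.1 schedules neuropsychological testing at T1, T3, T4 and T5, so the end-of-treatment score is the fourth administration in every arm.
- **Between-group (treatment) effect.** This is a valid comparison under randomisation, but it averages the end-of-treatment score with a score taken before randomisation. The estimated CRT effect is therefore half its true size at end of treatment.

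At stake is a first-phase trial whose continuation, under Section 10, requires improvement in the target. A shared gain could be credited to CRT, or a real CRT effect could be missed by the weakest of the available arm comparisons.

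**Working it through.** **Plan's own figure.** Section 6.4 prints no power for Aim 1, so there is nothing to reproduce. The .59 printed there belongs to the Aim 2 growth model.

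**Inputs from the plan.** Alpha .15 (Sections 6.1 and 6.4; taken as two-sided), correlation r = .3 and medium f = .25 (Section 6.4), 45 evaluable (Section 3.3.2), hence n = 15 per arm, as in the Aim 2 power text.

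**Assumptions.** The documents give no SDs or expected gains. I use unit SD, a shared gain c, and a CRT effect d at end of treatment. These are univariate approximations to the multivariate test, using the noncentral t.

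**1. Time effect when CRT does nothing.** SE = √(2(1−r)/N), with df N−2 for two arms and N−3 for three.

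- N = 30: SE = √(1.4/30) = 0.216. Gains of 0.3 and 0.5 SD give noncentralities 1.39 and 2.31, so P(significant) = .47 and .80.
- N = 45: SE = √(1.4/45) = 0.176. The same gains give 1.70 and 2.83, so .60 and .91.
- Gain of 0.2 SD: .31 (N = 30) and .38 (N = 45).
- With r = .7, a 0.3 SD gain gives .74 (N = 30) and .87 (N = 45).
- If *within* means change inside one CRT arm of 15 (SE = √(1.4/15) = 0.306, df 14): .32 and .56 for gains of 0.3 and 0.5 SD.

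Under the same null, the treatment effect, the interaction and the baseline-adjusted comparison all stay at .15. A simulation with IQ as covariate (20,000 runs, assumed correlation .3 with each score, 15 per arm) agrees: time .48 to .80, the other three .15.

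**2. Power when CRT works.** Two arms, n = 15 each, d = 0.5, r = .3:

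| Test | Estimate | SE | Noncentrality | Power |
|---|---|---|---|---|
| Treatment main effect | d/2 = 0.25 | √((2/n)(1+r)/2) = 0.294 | 0.85 | .28 |
| Treatment × time | d = 0.5 | √((2/n)·2(1−r)) = 0.432 | 1.16 | .39 |
| End of treatment, baseline-adjusted | d = 0.5 | √((2/n)(1−r²)) = 0.348 | 1.44 | .49 |

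At r = .5 the powers are .27, .47 and .55. At r = .7 they are .25, .62 and .67. The order does not change. At r = .3 the effect detectable with 80% power is 1.37, 1.00 and 0.81 SD respectively. For 80% power at d = 0.5, the number per arm is 109, 59 and 39.

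**3. The same comparison at the plan's f = .25.** For two arms, N = 30, the noncentrality λ is 30·2·.0625/1.3 = 2.88 for the treatment effect and 30·2·.0625/0.7 = 5.36 for the interaction. The powers are .59 and .80. On this scale f = .25 means a difference in gain of 4 × .25 = 1.0 SD, for which the baseline-adjusted comparison has power .92. With three arms, N = 45, the treatment effect has .64 and the interaction .85.

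**The case against.** The plan does not use the words main effects. *Between-group* could have been meant as the between-group difference in change, especially as the follow-ups compare FBT with CRT. In that case the intended contrast is the right one. It would then be the interaction, however, and the sentence would contradict itself, so it needs rewriting on either reading.

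The study could also be defended as a test of whether CRT moves the target, with efficacy expressly deferred (Sections 1.1 and 5.2). That does not help: a time effect that includes FBT-only participants cannot attribute movement to CRT, and Sections 1.3 and 2.1 name FBT alone as the comparator. The Aim 2 power text does define its effect as a slope above FBT, but only for the dose model.

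Four points stand as limits:

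- The Go/No-Go criteria are in Table 6, which is not in the available text and may include an arm comparison. The probabilities above are for a single time test. They are not probabilities of a wrong Go decision, and they leave out the omnibus step and the joint testing of several outcomes.
- The shared gain is assumed, and the result is sensitive to it. At 0.1 SD (N = 30, r = .3) the probability is only .19. The repeat-testing argument applies to the neuropsychological scores and not to the BRIEF-2 questionnaire scale.
- Halving the estimate overstates the loss, because averaging two scores also lowers the standard error. At r = .3 the treatment effect keeps 0.85/1.16 = 73% of the interaction's noncentrality and 0.85/1.44 = 59% of that of the baseline-adjusted test.
- Choosing baseline adjustment over the interaction is a matter of efficiency. Either resolves the mismatch.

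**Conclusion.** The concern holds: Section 6.1 is wrong as written. The conflict between the hypothesis and the effects to be read is in the plan's own text and depends on no numerical assumption. The size does. With r = .3 and 15 per arm, a gain of 0.3 to 0.5 SD that owes nothing to CRT would make the time effect significant in 47% to 80% of two-arm analyses. The between-group effect has the lowest power of the three arm comparisons at every correlation tried, and also at the plan's own f = .25 (.59, against .80 and .92). How far this would distort the Go/No-Go decision cannot be judged without Table 6.

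**What to change.** Delete the sentence in Section 6.1. Define the Aim 1 contrast as the arm difference at end of treatment, adjusted for the baseline value of the same measure and for WASI IQ. The treatment-by-time interaction is an acceptable, less efficient alternative. Apply the contrast to CRT_A against FBT in adolescents, and to CRT_P against FBT in mothers and in fathers. State that a time effect alone is not evidence that CRT engages the target. If the Table 6 criteria rely on the main effects, align them with this contrast.

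The cost is small. Baseline and end-of-treatment scores are already collected, and each model gains one covariate degree of freedom. At the plan's f = .25 the interaction already has power of .80 (two arms) to .85 (three arms), so the change does not by itself call for a larger sample. The a-priori Go/No-Go criteria may need rewording, and that must be settled before outcome data are examined.

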1.2 Name and Description of Investigational Product or Intervention

1.2.1 Family Based Treatment (FBT)

FBT is a manualized family treatment for adolescents with AN. It is effective for children and adolescents aged 12-18. It is a conjoint family treatment with all family members attending all sessions. For this study, we will use a 15 session version of FBT used in prior research. The goal of treatment is weight restoration and reduction of eating disorder symptoms. The primary focus of treatment sessions is to activate and empower the parents of the affected child to restore weight. Secondary goals of FBT include aligning the parental and sibling subsystems and reestablishing healthy adolescent developmental trajectories. Treatment will occur weekly at the beginning of treatment, move to bi-weekly, and then monthly for the last month of treatment. Families will have the option of receiving 12 additional FBT sessions after completing the first 15 sessions. These 12 sessions will be scheduled as families see fit and will occur over the course of six months.

The treatment takes place over 3 phases:

1. Refeeding and Weight Restoration
2. Returning Control of Eating to the Adolescent
3. Addressing Adolescent Issues and Treatment Completion

The PI has received training in the manual and has recently completed the necessary hours for certification in this treatment modality.

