3.3.2 Total Number of Study Sites/Total Number of Subjects Projected

The study will only be conducted at Children's Hospital of Philadelphia.

It is expected that approximately 60 subjects will be enrolled to produce at least 45 evaluable subjects.

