adolescents with AN. To determine optimal dose, we will model change across the 15 sessions using latent growth curve modeling (LGCM). LGCM will allow us to analyze individual and average trajectory and model linear and quadratic trend. We will visually assess for the point (dose) at which there is a significant decrease in the *rate* of improvement (quadratic). Parameter estimation will employ Maximum Likelihood (ML) estimation.^{93,94} We will evaluate model fit using chi-square (χ^2), Comparative Fit Index (CFI), Standardized Root Mean Squared Residual (SRMR), and Root Mean Squared Error of Approximation (RMSEA).⁹⁵ The following values are indicative of acceptable fit between the model and the observed data variance/covariance matrixes: CFI, SRMR, and RMSEA, $< .95$, $< .80$, and $< .05$, respectively. We will assess and compare different models using BIC and novel criteria such as Scaled Unit Information Prior BIC.^{96,97} Examining standardized model residuals in addition to global fit indices (GFI) permits us to identify model misspecification even if GFI values suggest adequate fit.⁹⁵

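### The Aim 2 dose rule in 6.1 and the Aim 2 target in 2.1 omit the FBT reference that the power calculation in 6.4 assumes, so any gain shared with FBT could be read as a CRT dose

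*Combined protocol and SAP*

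**What the plan says.** Section 2.1 sets the Aim 2 target: "We will examine the dose of CRT needed to obtain an increase in cognitive flexibility equal to a medium effect". No comparator is named.

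Section 6.1 gives the analysis, a latent growth curve over the 15 sessions: "LGCM will allow us to analyze individual and average trajectory and model linear and quadratic trend". The dose is then taken from the plot: "We will visually assess for the point (dose) at which there is a significant decrease in the" rate of improvement. No arm term, FBT reference curve or CRT-minus-FBT contrast appears. The Aim 1 text in the same section adds that interaction effects need not be examined.

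Section 6.4 describes the Aim 2 simulation differently. The effect is a half standard "deviation increase (rate of change; slope) from baseline (effect size) above FBT", the design is "With 15 participants in 3 groups across 5 time points", and the power is 0.59. The closing paragraph of section 1.3 also asks whether the increase exceeds the one seen with FBT alone.

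**The concern.** Sections 2.1 and 6.1 describe an increase; section 6.4 describes an increase relative to FBT. The two agree only if nothing changes under FBT alone.

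The design ties CRT dose to other things. Section 1.2.2 places each CRT session before an FBT session, 15 in all, and FBT also has 15 sessions. Within a CRT arm, the CRT session count therefore rises with the FBT session count. It also rises with calendar time, on a tapering schedule ("Treatment will occur weekly at the beginning of treatment, move to bi-weekly, and then monthly for the last month of treatment"), and with test exposure: the D-KEFS is given at baseline and three later visits, and alternate forms are not mentioned. Only the FBT arm can separate these from CRT.

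The documents suggest that some shared gain is possible. Section 2.1 hypothesises greater increases than under FBT alone. Section 1 says that set-shifting does not recover fully with re-nourishment, which implies partial recovery. Section 1.3 allows for a stress-related loss of flexibility in parents, which might ease as the child recovers.

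Section 10 makes this the first of two phases. A dose reflecting FBT, time and retesting could inform the design of the second.

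**Working it through.** **1. The plan's own figure.** Section 3.3.2 expects "approximately 60 subjects will be enrolled to produce at least 45 evaluable subjects", and 45/3 = 15 per arm, as in 6.4. The 0.59 cannot be reproduced uniquely, because the growth-factor and residual variances, the alpha and the sidedness of the simulation are not stated. A CRT-versus-FBT contrast in linear slopes can be checked using the correlation of 0.3 and alpha of 0.15 from the Aim 1 paragraph:

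- Five equally spaced times scaled to 0–1: S = Σ(t − t̄)² = 0.625.
- SE = √[2(1 − 0.3)/(15 × 0.625)] = 0.386, so 0.5/0.386 = 1.294.
- Power, two-sided 0.15: Φ(1.294 − 1.440) = 0.44.
- Power, one-sided 0.15: Φ(1.294 − 1.036) = 0.60.

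The one-sided value is close to 0.59. An above-FBT slope contrast is thus a plausible basis for the figure. Other assumed variances also reach about 0.59, so the match is not proof.

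**2. Inputs for the dose rule.** Section 6.1 does not name the Aim 2 outcome; I assume the Aim 1 neurocognitive measures. Section 4.2.1 lists treatment visits 1–8, 10–12 and 14–17, with testing at visits 0, 9, 13 and 18. That places the assessments after 0, 8, 11 and 15 sessions. Other assumptions: 15 per arm, SD 1, correlation 0.3, a quadratic fit, zero CRT effect, and a gain by session 15 shared by both arms.

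The rule in 6.1 is visual, so a numerical stand-in is needed. A dose is declared if the session-15 gain is significant (two-sided 0.15, positive direction, so 7.5%) and the fitted curve reaches 0.5 SD.

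**3. Approximation by hand.** With c′(X′X)⁻¹c = 1.90 for the fitted gain at session 15:

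- One arm: variance = (0.7/15) × 1.90 = 0.0887, SE = 0.298. Significance needs 1.44 × 0.298 = 0.43 SD, so the 0.5 SD threshold governs.
- CRT minus FBT: variance = 2 × 0.0887 = 0.177, SE = 0.421. Significance needs 1.44 × 0.421 = 0.61 SD, so significance governs and the rate is about 7.5% whatever the shared gain.

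For the single arm, P ≈ Φ((g − 0.5)/0.298), where g is the shared gain.

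| Shared gain g (assumed) | Own curve, by hand | Own curve, simulated | CRT minus FBT, simulated |
|---|---|---|---|
| 0 | Φ(−1.68) = 5% | about 4% | about 7% |
| 0.25 SD | Φ(−0.84) = 20% | about 21% | about 7% |
| 0.5 SD | Φ(0) = 50% | about 51% | about 7% |
| 0.75 SD | Φ(0.84) = 80% | about 80% | about 7% |

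**4. Sensitivity.** With five assessments (sessions 0, 4, 8, 12, 15), the own-curve rates are 3–4%, 19–20%, 52% and 83%, against 7–8% for the contrast. A second stand-in is closer to the wording of 6.1: a significant gain with a positive linear and a negative quadratic term. With a flattening shared gain of 0.5 SD and five assessments, it finds a plateau in 46% of trials on the own curve and 4% on the contrast.

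**The case against.** The strongest reply is that the plan is silent, not wrong. Section 6.1 does not say which curves are read. Section 6.4 simulates the same growth model with three groups and an effect above FBT, and section 1.3 states a goal relative to FBT. A reader might infer that the plan has chosen to read the dose from the CRT arm alone and to disregard FBT. The documents do not support that; they show an FBT-relative intent that 2.1 and 6.1 fail to carry. This part of the reply stands.

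A reader might also infer that an inert CRT could simply pass into the next phase with a dose attached. That goes too far as well. Aim 1 plans comparisons of FBT with the relevant CRT arm, these inform the Go/No-Go decision, and section 10 requires its criteria to be met. This limits the consequence. It does not remove it: Aim 1 tests at alpha 0.15, and Aim 2 is not made conditional on it. Table 6, which holds the criteria, is not in the text available to me.

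The mechanisms also differ by role and measure. Re-nourishment does not act directly on parents' own scores, and BRIEF-2 Shift is a rating, so test practice does not carry over to it directly. No source of shared gain has a stated size. With no shared gain, the own-curve rule is not inflated at all (about 4%).

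What remains is that an analyst following 6.1 as written has no instruction to subtract FBT, and the dose cannot be attributed to CRT without it.

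**Conclusion.** The concern holds as an inconsistency with practical consequences: 2.1 and 6.1 leave out the FBT reference that 6.4 and the goal in 1.3 rely on. Under zero CRT effect, the chance of declaring a dose from the CRT arm's own curve rises from about 4% to about 80% as the assumed shared gain goes from 0 to 0.75 SD. From CRT minus FBT it stays at about 7%.

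These rates rest on assumed shared gains, a numerical substitute for a visual rule, 15 evaluable per arm, and a correlation borrowed from the Aim 1 paragraph. They show how the rule behaves; they do not predict this trial. Because the FBT-relative intent is visible and Aim 1 gives partial protection, this is a should-fix point, best settled before the Aim 2 data are examined.

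**What to change.** In 6.1, include treatment arm in the growth model, with arm-by-linear-time and arm-by-quadratic-time terms, separately for adolescents, mothers and fathers. Read the Aim 2 dose from the role's own CRT arm minus FBT at the same visits, with a confidence interval. Reword the Aim 2 target in 2.1 so that the increase is above FBT, as in 6.4.

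State in advance what happens if the interval is too wide to locate a dose: report the dose as descriptive, with the FBT curve shown alongside. This may well be needed. Under the inputs above, the 85% interval for the session-15 difference has a half-width of 1.44 × 0.421 = 0.61 SD, wider than the half-SD target.

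The change is wording only, because the FBT arm is already assessed at the same visits. The cost is precision: the difference has about twice the variance of one arm's curve. That cost is already in the plan, since the stated power of 0.59 is for an effect above FBT.

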1.2.2 Cognitive Remediation Therapy

CRT is an adjunctive intervention focusing on the development of meta-cognition – teaching individuals to think about how they think.⁴⁴ It involves presenting individuals with a variety of

tasks requiring increasingly complex mental abilities – these include geometric figures, illusions, reversing sequences of numbers and letters, completing sorting tasks wherein the rules change, and finding various routes on a map.⁴⁵ Most importantly, CRT focuses on process instead of outcome. That is, instead of focusing on whether or not a task was accurately completed, individuals in CRT are asked to think about how they solved a puzzle, reflect on their thought processes, and identify steps in problem solving. CRT has three goals:

1. Improve brain function by exercising and increasing connections in the brain
2. Encourage individuals to think about their thinking style
3. Encourage individuals and families to spend time away from thinking about the eating disorder.

CRT can be delivered in individual, family, and group formats.⁴⁶⁻⁴⁸ For this study, we will administer CRT to either adolescents or their parents. CRT will be delivered for 45-60 minutes prior to FBT sessions for a total of 15 sessions. Participants in CRT will be given weekly homework.

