4.2.1 Visit 1-8, 10-12, 14-17

Each visit the family will receive the treatment assigned during randomization (FBT, CRT_P, or CRT_A). The following will happen at each session:

- Height and weight
- Review of homework
- Study intervention
- Medical Record Review (without participants)

4.2.2 Visit 4

- Questionnaires (online or in-person)
- Height and weight
- Medical Record Review (without participants)

4.2.3 Visit 9

- Medical Record Review (without participants)
- Height and weight
- Questionnaires (online or in-person)
- Neuropsychological testing

4.2.4 Visit 13

- Medical Record Review (without participants)
- Height and weight
- Questionnaires (online or in-person)
- Buffet Challenge
- Howe's Grocery
- Neuropsychological testing

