Detail and Flexibility Questionnaire (DFlex;⁸⁰). The DFLEX is a 24-item self report measure assessing cognitive rigidity and attention to detail, both considered aspects of neurocognitive functioning. Both aspects have been measured in an Autistic sample using the Autism Spectrum Quotient (AQ), and thus the AQ was used to determine construct validity. A strong correlation for cognitive rigidity was shown ($r = .72$) and a moderate correlation for attention to detail ($r = .26$). The DFLEX is a new measure developed to address both flexibility and central coherence. It will be completed by parents and adolescents.

Line Bisection Task (LBT;⁸¹). The LBT has been widely used as a behavioral measure of visual neglect in patients with brain damage. More recently, neuroimaging research has confirmed it can also be used to measure approach motivation in non-clinical populations. In the task participants mark the perceived mid-point of staggered horizontal lines of the same length in millimeters (mm). When participants make errors in marking the midpoint left of the true midpoint these are scored as negative. Meanwhile, positive scores mean greater left to right hemisphere activation. The LBT is being piloted in this study as a behavioral measure of approach-based coping. It will be completed by both adolescent and parents.

Family Questionnaire (FamQ;⁸²). Expressed emotion (EE) has traditionally been assessed via clinical interview, however the interview can be laborious and time consuming. In order to address this issue, the FQ was developed. It is a 20 item self-report measure that includes two subscales: criticism and emotional over involvement. Scores on the FQ have high convergent validity with more traditional interview assessments of EE. Test-retest reliability over two weeks produced Pearson correlations of $r= 0.84$ for the criticism (CC) and $r=0.91$ for the emotional overinvolvement (EOI) subscales. Similarly, internal consistency was good, ranging from 0.90-0.92 for the CC and 0.79-0.82 for the EOI subscales. Only parents will complete this measure.

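### Aim 2 asks for the CRT dose that gives a medium effect, but its only dose rule looks by eye for where improvement slows, which does not show whether or when a medium effect is reached

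*Combined protocol and SAP*

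**What the plan says.** Section 2.1 sets the target: "We will examine the dose of CRT needed to obtain an increase in cognitive flexibility equal to a medium effect". Section 6.1 repeats it: "Aim 2: To determine the dose of CRT needed to lead to a medium effect size". Both place Aim 2 among the primary aims.

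The method is in section 6.1. A latent growth curve model (LGCM) with linear and quadratic trend is fitted across the 15 sessions, and then: "We will visually assess for the point (dose) at which there is a significant decrease in the" rate of improvement. The rest of the Aim 2 text covers estimation, fit indices and model comparison by BIC. It names no outcome, effect-size threshold, CRT-versus-FBT contrast by session or interval for the dose.

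Section 6.4 does put a number on the effect, as an input to the Aim 2 power simulation: half a standard "deviation increase (rate of change; slope) from baseline (effect size) above FBT". The simulation is described as "With 15 participants in 3 groups across 5 time points", with a stated power of 0.59.

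**The concern.** The target and the rule are different quantities. The target is a level: the session by which flexibility has improved by a medium amount. The rule looks for a change in pace: the session at which improvement slows. A small gain can slow early and a large gain may not slow at all.

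Followed as written, the plan can name a session count when no medium effect occurred. It also gives no way to see how uncertain that count is. What is at stake is the Aim 2 dose conclusion. The inputs to the Go/No-Go decision that can be seen in section 6.1 come from Aim 1.

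**Working it through.** **The plan's own figure.** The power of 0.59 can be neither confirmed nor refuted, because section 6.4 does not give the LGCM variances. Reading the sample as 15 per group (3 × 15 = 45, the evaluable number in section 3.3.2), I took a linear growth model with five equally spaced times and a total slope difference of 0.5 SD. Over assumed intraclass correlations of 0.3 to 0.8 and slope variances of 0 to 0.5, power for 15 against 15 is 0.36 to 0.84 at two-sided alpha 0.15. So 0.59 is attainable. It concerns a slope difference above FBT and does not describe the visual rule.

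**What slowing means on a quadratic.** Let the gain after t sessions be b1·t + b2·t², in baseline SDs.

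- Rate of improvement: b1 + 2·b2·t. It changes by the same 2·b2 at every session, so no session stands out as the start of slowing.
- Turning point: −b1/(2·b2). Multiplying the whole curve by a constant leaves it unchanged.
- The curvature b2 does grow with the gain. Only the location of the turning point is free of it.

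**Illustration (all curves assumed).** For a total gain G that levels off at session 15, b1 = 2G/15 and b2 = −G/225. The turning point is (2G/15)/(2G/225) = 15 for every G. Setting the gain equal to 0.5 SD:

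| G (SD) | Equation | 0.5 SD reached at |
|---|---|---|
| 0.30 | maximum is 0.30, below 0.5 | never |
| 0.75 | t² − 30t + 150 = 0; t = 15 − √75 | session 6.3 |
| 1.50 | t² − 30t + 75 = 0; t = 15 − √150 | session 2.8 |

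A straight line of 0.05 SD per session gains 0.75 SD over 15 sessions and crosses 0.5 SD at session 10, with no slowing to see.

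**Adding FBT.** Every arm receives FBT. With an assumed linear FBT gain F over 15 sessions, the advantage is (b1 − F/15)·t + b2·t².

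- G = 0.75, F = 0.15: t² − 27t + 150 = 0, so t = 13.5 − √32.25 = 7.8.
- G = 0.75, any F: a solution needs 300·(0.1 − F/15) ≥ 2√150 = 24.49, that is F ≤ about 0.275 SD. Above that, a 0.5 SD advantage is never reached.

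A reading of the CRT curve alone cannot show this.

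**Time points.** Section 6.4 assumes five. Sections 3.3.1 and 4.2.2 list no neuropsychological testing at T2 (Visit 4), and Table 1, as extracted, shows none for BRIEF-2 there either. The section 6.1 measures are therefore taken at four points through end of treatment: baseline, Visit 9, Visit 13 and Visit 18. Section 4.2.1 places treatment at "Visit 1-8, 10-12, 14-17", so these fall after 0, 8, 11 and 15 sessions. The curve before Visit 9 is not observed for these measures.

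**The case against.** The strongest reply is that the LGCM can answer the question, and that section 6.4 already links dosage to half an SD above FBT. Both statements are true. The model is suitable and the plan does have a numeric medium effect with an FBT comparator. What is missing is the step that carries them into the rule in section 6.1.

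A second reply is that this is a target-engagement phase in which section 5.2 disclaims any efficacy evaluation. That limits the consequences, but the plan itself lists Aim 2 as primary.

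Some stronger readings are tempting, and the documents do not support them:

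- A reader might infer that the rule returns no dose when improvement is a straight line. The plan models linear trend as well and simply does not say what would be reported.
- A reader might treat the decrease as a formal test of the quadratic term and criticise its power. The text says the assessment is visual and attaches no test. Even if a test were meant, it would show curvature, not a session.
- A reader might infer that the Go/No-Go decision is compromised. Section 6.1 cites Table 6 for that decision only under Aim 1, and the table is not in the supplied text, so a dose criterion there can be neither confirmed nor excluded.

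**Conclusion.** The concern holds on the plan's own wording. The stated target is the dose that gives a medium effect, while the only dose rule locates slowing, by eye and without an interval. The algebra does not depend on the illustrative curves. The session numbers do: they assume quadratic CRT curves levelling off at session 15, a linear FBT gain and 0.5 SD as the medium effect. Under those assumptions, one shared turning point is compatible with reaching 0.5 SD never, at session 6.3 or at session 2.8.

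The defect lies in the decision rule, not in the choice of LGCM, and the stated power of 0.59 is not shown to be wrong. Separately, the five time points behind that figure do not match the four at which the section 6.1 measures are taken. The rule should be changed before the Aim 2 analysis.

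**What to change.** Replace the visual rule with a read-off from the planned LGCM, and keep any slowing as description only.

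1. Define the dose as the smallest number of sessions at which the model-implied CRT-minus-FBT difference reaches 0.5 baseline SD. Compare arms at the same FBT session number, which is workable because "CRT will be delivered for 45-60 minutes prior to FBT sessions for a total of 15 sessions".
2. Name one section 6.1 measure in advance, and apply the rule separately to CRT_A adolescents, CRT_P mothers and CRT_P fathers.
3. Report a family-level bootstrap interval at a pre-stated level, for example 90%.
4. Allow the result *not reached within 15 sessions*, and report *dose not established* when the interval includes it.
5. Flag any crossing before the first repeat assessment (Visit 9) as interpolated.
6. Restate the number of time points in the Aim 2 power statement to match the chosen measure.

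The cost is SAP wording and a bootstrap for three respondent groups, with the same data and visits. Some bootstrap fits may not converge at about 15 per arm.

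The low yield should be disclosed. I simulated the read-off with 15 per arm, correlation .3 (given in section 6.4 for Aim 1), an FBT gain of 0.15 SD and known covariance, which is optimistic. Assessments were after 0, 8, 11 and 15 sessions, with or without one after session 4.

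| True CRT gain | Dose established, 95% interval | Dose established, 90% interval |
|---|---|---|
| 0.75 SD | about 15-16% of trials | about 23-26% |
| 1.50 SD | about 96% | about 98% |
| 0.30 SD | about 1% at most | about 1% |

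Without the interval, the 0.30 SD curve would appear to cross 0.5 SD in about 22-26% of trials. The crossing point should therefore never be reported alone.
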